### **Primary objective 2**

**To describe the preliminary feasibility of measuring the safety of mobilising ICU patients receiving vasoactive drugs.**

#### Secondary objectives

##### 2 a) Recruitment

1. To measure the number of patients who would consent in principle to be recruited into an RCT on the safety of mobilising patients receiving vasoactive drugs and to describe the reasons why patients would not consent.
2. To understand the acceptability to patients and clinicians, of randomising patients receiving vasoactive drugs to an intervention or control arm in a future RCT on the safety of mobilising patients receiving vasoactive drugs.
3. To test the feasibility of clinicians and clinician researchers taking informed consent from patients or their consultees on ICU.

2 b) Sample size

1. To measure mortality, disability, physical functioning and health related quality of life outcome measures of ICU patients to inform a future sample size calculation.

2 c) Outcomes

1. To describe the feasibility of measuring mortality, physical functioning, disability and health related quality of life outcomes to inform a future primary outcome choice.
2. To measure whether an adverse event tool captures all unsafe events that occur during or immediately after early mobilisation of adult intensive care patients receiving vasoactive drugs.
3. To describe the feasibility of an adverse event tool, during clinical practice by ICU clinicians and retrospectively by researchers.

[figure not shown]

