#### **5.5 ANALYSIS OF MOBILISATION**

Whenever a physiotherapist reviews a patient recruited into the feasibility study for potential physical rehabilitation whilst they are receiving vasoactive drugs, they will complete an extra proforma in the case notes. This will record the following data to provide information on the decision-making process on the readiness of a patient to mobilise and the feasibility of using an adverse event tool:

- Who made the final decision whether to mobilise the patient and the reasons for the decision.
- Was the presence of vasoactive drugs a factor in the decision of whether to mobilise, either from the perspective of clinicians or in discussion with the patient/family/carers themselves?
- If a mobilisation treatment is carried out the following will also be completed:
  - The reasons why the mobilisation treatment was stopped. This is measured to capture clinicians perceived risk thresholds for discontinuing mobilisation. This informs the measurement of the usability of the adverse event tool.

- An ICU physical rehabilitation adverse event tool used to measure adverse events that occur during or immediately after the mobilisation treatment. This is a new adverse event tool developed by the authors using an international, expert consensus Delphi process (IRAS project ID: 212066; REC reference: 17/LO/0830). The tool outlines specific adverse events including cardiovascular, respiratory, neurological, airway, attachments, falls and injury related events agreed as important to record when measuring the safety of ICU mobilisation.
- The approximate time taken to complete the adverse event tool to inform the assessment of its feasibility. Feasibility success is defined as less than 5 minutes

Alongside this, a case note review will be completed by the research team for each mobilisation treatment of patients receiving vasoactive drugs enrolled into the feasibility study. The researcher will record ICU physical rehabilitation adverse events and serious adverse events that occur during or immediately after mobilisation treatment. The following outcomes will then be measured:

- ICU rehabilitation adverse event rate and SAE rate. SAEs will be measured during the note review and as reported by clinicians and researchers during the study as part of the mandated safety reporting. This will highlight the most efficient way to collect SAEs and both measures will inform a description of the safety of usual care.

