- Description of the number and type of rehabilitation adverse events and serious adverse events. Recorded to measure whether the rehabilitation AE tool is fit for purpose and able to capture all unsafe events that occur in this population of patients mobilising on vasoactive drugs.
- Description of number and type of rehabilitation adverse events recorded prospectively by the treating clinician and retrospectively by researcher case note review. This data will provide information on the usability of the tool and the most feasible way to record AE's in future research.
- Loss of information that occurs when the ICU rehabilitation AE tool is completed by clinicians and researchers will also be recorded to provide feasibility data. For clinicians this will be assessed by the number of mobilisation treatments on vasoactive drugs occurring in patients recruited into the feasibility study where the rehabilitation adverse event tool is not completed or incomplete. For researchers, this will be assessed by the number of mobilisation treatments on vasoactive drugs where the researcher was unable to complete tool using the information available in the case notes. Feasibility success is less than or equal to 10% loss of information.

Towards the end of the data collection period for patients on ICU, a short survey will be carried out of clinicians who completed the ICU rehabilitation adverse event tool. This survey will ask about the usability and feasibility of completing the AE tool in the context of clinical practice.

In addition to the above, the following data will be recorded for participants to further quantify standard care:

- Amount of time the patient received vasoactive drugs during the admission.
- Mobilisation occurring whilst patients are receiving vasoactive drugs, for example, by:
  - Number of patients who are mobilised whilst receiving vasoactive drugs.
  - Number of mobilisation treatment sessions on vasoactive drugs.
  - Number of days on vasoactive drugs where mobilisation treatment occurred.
  - Highest level of mobilisation achieved in each treatment session using the ICU Mobility Scale (IMS) (Hodgson et al., 2014a, Tipping et al., 2016).
  - Type and dose of vasoactive drugs patient received during mobilisation treatment.
- Patients receiving vasoactive drugs who are not mobilising, for example, by:
  - Number of days receiving vasoactive drugs where mobilisation is not occurring.

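### Whether the tool captures all unsafe events is judged against the tool's own categories plus SAEs, so completeness is likely to be overestimated

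*Combined protocol and SAP*

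**What the plan says.** Section 2, objective 2 c) item 2, is worded as a test of completeness: "To measure whether an adverse event tool captures all unsafe events that occur during or immediately after early mobilisation of adult intensive care patients". The text goes on to specify those receiving vasoactive drugs.

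Section 5.5 describes the instrument as the product of an earlier Delphi process: "The tool outlines specific adverse events including cardiovascular, respiratory, neurological, airway, attachments, falls and injury related events". The physiotherapist completes it after each mobilisation treatment given on vasoactive drugs. Alongside this, the research team reviews the case notes for each such treatment: "The researcher will record ICU physical rehabilitation adverse events and serious adverse events that occur during or immediately after mobilisation treatment".

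The outcome tied to the objective is a description of the number and type of these two classes of event: "Recorded to measure whether the rehabilitation AE tool is fit for purpose and able to capture all unsafe events that occur in this population". A second outcome compares what the clinician recorded prospectively with what the researcher found in the notes, and is meant to inform usability and the best way to record events. A third, loss of information, shows that the researcher fills in the same tool: for researchers it counts treatments "where the researcher was unable to complete tool using the information available in the case notes".

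On serious events, section 5.5 adds: "SAEs will be measured during the note review and as reported by clinicians and researchers during the study as part of the mandated safety reporting".

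**The concern.** Completeness of capture is a proportion. Its denominator is all unsafe events, including those the tool does not list, so it needs a record of events made without reference to the tool. The plan has one for serious events only. Clinician and researcher otherwise work from the same list, and agreement between them shows that the list is applied consistently, not that it is complete.

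A non-serious unsafe event that is absent from the list and does not end the session has no planned route into the data, as far as the visible text shows. Such events drop out of the denominator, and the error favours the tool. This matters because the study is meant to prepare for a randomised trial whose question is safety (section 1.2), and because the same section names varied adverse event criteria and poor recording as weaknesses of earlier studies.

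**Working it through.** The plan gives no capture rate, event rate or expected number of events, so there is no figure to reproduce. The check has two parts.

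**1. Which channels could show an off-list event?**

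- *Rehabilitation adverse events (section 5.5).* These have no definition separate from the tool, so they cannot show what the tool leaves out.
- *SAEs (sections 5.5 and 7.1).* These are defined independently of the tool and named for this outcome. The definition is wide in one respect, since it extends to important events that could endanger the patient or call for preventive intervention. It is narrower in another, since it requires the event to be unexpected. Non-serious events stay outside it.
- *General safety reporting (section 7.2).* This is limited to events related to study procedures involving participant contact. Mobilisation is usual care here, so it is not covered. This also sits awkwardly with the reliance in section 5.5 on mandated safety reporting as a second source of SAEs; the two sections need reconciling.
- *Reasons for stopping (section 5.5).* These are recorded for each mobilisation treatment and do not depend on the list. They could reveal an off-list event that ended a session, but they are assigned to clinicians' risk thresholds and to usability, not to capture.
- *Clinician survey (section 5.5).* It covers usability and feasibility; no question on missed events is described.
- *Analysis (section 8).* It is descriptive. No capture proportion, denominator or success criterion is set, although section 5.5 sets criteria for completion time (under 5 minutes) and loss of information (at most 10%).

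**2. How large could the overestimate be?**

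All three inputs are assumptions:

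- f = share of unsafe events that are off-list
- s = share of off-list events that are serious
- q = share of non-serious off-list events that surface through stop reasons

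Assume also that every on-list event is recorded and that the note review finds every off-list SAE. Then:

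- True capture = 1 − f
- Apparent capture = (1 − f) / [(1 − f) + f·s + f·(1 − s)·q]

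The denominator cannot exceed 1, so under these assumptions apparent capture is never below true capture.

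Take f = 0.20 and s = 0.10. On-list events are 0.80, serious off-list 0.20 × 0.10 = 0.02, and non-serious off-list 0.20 × 0.90 = 0.18. True capture is 80%.

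| q | Denominator | Apparent capture |
|---|---|---|
| 0 | 0.80 + 0.02 = 0.82 | 97.6% |
| 0.25 | 0.82 + 0.045 = 0.865 | 92.5% |
| 0.5 | 0.82 + 0.09 = 0.91 | 87.9% |
| 1 | 0.82 + 0.18 = 1.00 | 80.0% |

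With stop reasons unused (q = 0), over f = 5% to 40% and s = 5% to 50%:

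- Highest apparent capture: f = 0.05, s = 0.05 gives 0.95/0.9525 = 99.7%, against a true 95%.
- Lowest apparent capture: f = 0.40, s = 0.50 gives 0.60/0.80 = 75.0%, against a true 60%.
- Largest overestimate: f = 0.40, s = 0.05 gives 0.60/0.62 = 96.8%, against a true 60%.
- Smallest overestimate: f = 0.05, s = 0.50 gives 0.95/0.975 = 97.4%, against a true 95%.

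**The case against.** The strongest reply is that the instrument cannot be seen. The tool, the proforma and the note-review form are not reproduced, and section 5.5 introduces the event categories as examples. A free-text or 'other' line may already exist. That stands as a limit on this point. Section 5.5 describes no such field, however, and no analysis is prespecified that would turn its entries into a capture result.

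Second, a reader might infer that off-list non-serious events go wholly unseen. The documents do not support this: stop reasons are collected for each mobilisation treatment, so an off-list event that ended a session would be recorded somewhere.

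Third, a reader might infer that capture must come out near complete by construction, or that the objective cannot be answered at all. Neither follows. SAEs are named for this outcome and could show that the tool failed. In the illustration apparent capture falls as low as 75.0% with stop reasons ignored. A figure of 100% would arise only if every off-list event were non-serious and none surfaced through stop reasons.

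Fourth, some events that are off-list, non-serious and do not end a session may not count as unsafe in the sense of the objective. That is fair, but the plan gives no way to tell how many there are or what they were.

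Last, this is a secondary objective and not one of the two key outcomes in section 5.3, and the analysis is descriptive with no pass mark for capture. This limits the consequence of the bias but does not remove it.

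**Conclusion.** The point holds in a limited form. The plan sets out to measure completeness but prespecifies no independent reference for non-serious off-list events. The objective can be answered in part, through SAEs and, if they were used for this purpose, stop reasons. It cannot be answered fully, and the result is likely to lean towards the tool.

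The size is unknown. With f = 20% and s = 10%, the overestimate is about 18 percentage points if stop reasons are unused and about 8 if half of the non-serious off-list events surface through them. Over the range examined with stop reasons unused, it runs from about 2 to 37 points. These figures rest wholly on assumed shares and on full recording of on-list events and off-list SAEs. They would shrink or vanish if the unseen form already has a free-text field that is completed and analysed.

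**What to change.** Change the case-note review in section 5.5 as follows.

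1. For each mobilisation treatment, the researcher first records in free text any untoward event, using the adverse event definition in section 7.1, that is documented during the session or immediately afterwards. Only then is each event coded as on or off the tool's list.
2. Classify the stop reasons already being collected as on-list or off-list.
3. Report the number and proportion of off-list events as the capture result, with a confidence interval that allows for several sessions per patient.
4. State as a limitation that case notes may omit minor events and that a researcher who knows the list is not a fully independent observer.

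If a line for other untoward events is added to the clinician proforma, keep it outside the timed tool so that the 5-minute criterion is unaffected. If such a line already exists, say so and prespecify how it will be analysed. Sections 5.5 and 7.2 should also be reconciled on whether safety reporting will supply SAEs from usual-care mobilisation.

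This is a cheap improvement: one free-text field and one coding step in a review already planned for each session, with the same notes and staff. The downside is a little more review time per session.

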# 7. ADVERSE EVENTS

## 7.1 DEFINITIONS

**Adverse Event (AE):** any untoward medical occurrence in a patient or clinical study subject.

**Serious Adverse Event (SAE):** any untoward and unexpected medical occurrence or effect that:

- **Results in death**
- **Is life-threatening** – *refers to an event in which the subject was at risk of death at the time of the event; it does not refer to an event which hypothetically might have caused death if it were more severe*
- **Requires hospitalisation, or prolongation of existing inpatients' hospitalisation**
- **Results in persistent or significant disability or incapacity**
- **Is a congenital anomaly or birth defect**

Medical judgement should be exercised in deciding whether an AE is serious in other situations. Important AEs that are not immediately life-threatening or do not result in death or hospitalisation

but may jeopardise the subject or may require intervention to prevent one of the other outcomes listed in the definition above, should also be considered serious.

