## 7.2 REPORTING PROCEDURES

All adverse events should be reported. Depending on the nature of the event the reporting procedures below should be followed. Any questions concerning adverse event reporting should be directed to the Chief Investigator in the first instance. This study is observational (not involving changes to standard care) therefore we will only monitor for and report AEs and SAEs that are related to study procedures which involve contact with the participant.

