### 7.2.2 Serious AEs

An SAE form should be completed and emailed to the Chief Investigator within 24 hours. However, relapse and death due to pre-existing conditions, and hospitalisations for elective treatment of a pre-existing condition do not need reporting as SAEs.

All SAEs should be reported to the Wales Research Ethics Committee 6 where in the opinion of the Chief Investigator, the event was:

- 'related', ie resulted from the administration of any of the research procedures; and
- 'unexpected', ie an event that is not listed in the protocol as an expected occurrence

Reports of related and unexpected SAEs should be submitted within 15 days of the Chief Investigator becoming aware of the event, using the NRES SAE form for non-IMP studies. The Chief Investigator must also notify the Sponsor of all SAEs.

Local investigators should report any SAEs as required by their Local Research Ethics Committee, Sponsor and/or Research & Development Office.

Contact details for reporting SAEs

[[contact]](mailto:[contact])

CI email (and contact details below)

Please send SAE forms to: [REDACTED]

Tel: [REDACTED] (Mon to Fri 09.00 – 17.00)

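### Section 5.5 uses mandated safety reports as a second source of mobilisation SAEs, but section 7.2 restricts those reports in a way that leaves such events out, and section 7 is not consistent within itself

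*Combined protocol and SAP*

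**What the plan says.** Section 5.5 describes the first source, the case note review, as follows: "The researcher will record ICU physical rehabilitation adverse events and serious adverse events that occur during or immediately after mobilisation treatment". It then adds a second source, SAEs "as reported by clinicians and researchers during the study as part of the mandated safety reporting". It gives the reason for having two: "This will highlight the most efficient way to collect SAEs and both measures will inform a description of the safety of usual care".

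The scope of the second source is set in section 7. Section 7.2 opens with "All adverse events should be reported". The same paragraph goes on to say that, because the study is observational, "we will only monitor for and report AEs and SAEs that are related to study procedures which involve contact with the participant".

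Section 7.2.2 works in steps. An SAE form goes to the Chief Investigator within 24 hours. Events go on to the ethics committee only if they are judged both related to the research procedures and unexpected. The Sponsor is treated differently: "The Chief Investigator must also notify the Sponsor of all SAEs". There is also an exemption: "relapse and death due to pre-existing conditions, and hospitalisations for elective treatment of a pre-existing condition do not need reporting as SAEs". The only SAE definition in the protocol, in section 7.1, begins "any untoward and unexpected medical occurrence or effect that" and then lists the seriousness criteria.

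**The concern.** Two ways of collecting an event can be compared only if both are looking for that event. Section 5.5 asks the safety reports to yield SAEs of mobilisation. The restrictive sentence in section 7.2 tells staff to report something else. If staff follow it, the study could conclude that note review collects SAEs better when all it has observed is that the reports were not meant to contain them.

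The study is preparing for a randomised trial, so a conclusion on how to collect SAEs may be carried forward. The adverse event rate during mobilisation on vasoactive drugs is also one of the secondary objectives in section 2. There is a practical side too: from sections 7.2 and 7.2.2 together, a clinician who sees an SAE during mobilisation cannot tell whether a form is due.

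**Working it through.** The plan states no SAE rate, and no sample size depends on one, so there is no figure to reproduce. The check sets the texts side by side.

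**Step 1. What each source covers.** Section 5.5 ties note review to events in or just after a mobilisation session. It gives the reports no scope of their own, so their scope has to come from section 7.

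**Step 2. Whether mobilisation is a study procedure.** Section 3 presents the mobilisation sessions as routine treatment that the study analyses. Section 7.2 justifies its restriction by saying that standard care does not change, and section 9.1 says the same. Mobilisation is therefore observed, not applied by the study. The protocol does not list the procedures that count as contact. Section 9.1 discusses the time burden of the initial survey and the day-60 measures, but it is not offered as that list. The argument needs only that routine mobilisation is not a study procedure.

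**Step 3. The two readings of section 7.**

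| | Restrictive sentence of 7.2 governs | Opening of 7.2 and the steps of 7.2.2 govern |
|---|---|---|
| SAE of routine mobilisation, note review | in scope | in scope |
| SAE of routine mobilisation, safety reports | out of scope | in scope, unless exempted by 7.2.2 |
| SAE of the day-60 walk test, note review | out of scope | out of scope |
| SAE of the day-60 walk test, safety reports | in scope | in scope |
| Meaning of a difference in counts | reporting scope | interpretable once the sources are aligned |

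**Step 4. Restrictive reading.** The two sources look for different events. Section 5.5 does not define efficiency. Whether it means yield, effort or timeliness, the comparison fails, because it is not made on a common set of events.

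**Step 5. Broad reading.** Section 7.2.2 supports it. If only procedure-related events entered the channel, the relatedness test at the ethics committee step would have nothing to remove, and there would be little reason to exempt deaths and relapses from pre-existing conditions. On this reading the comparison can work, but three things must match:

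- the time window, since section 7 reports are not confined to mobilisation sessions;
- the exemptions, since 7.2.2 applies them to reports and nothing applies them to note review;
- the SAE definition, since 5.5 does not say that note review uses the one in 7.1.

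**Result.** Under one reading the comparison in 5.5 measures reporting scope. Under the other it needs alignment that the plan does not spell out. The text does not settle which reading applies.

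**The case against.** The strongest reply is that section 7.2.2 makes sense only if unrelated SAEs are reported. The restrictive sentence would then be loose drafting, and 5.5 would work as intended. On this view the window in 5.5 can be read as governing the whole SAE outcome, since the outcome list follows directly after the sentence that sets the window. Section 7.1 holds the only SAE definition, so note review would naturally use it. Limiting safety reports can also be a reasonable choice when standard care is unchanged.

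Much of this stands. The conflict lies inside section 7 at least as much as between 5.5 and 7.2. The window and the definition may well be intended to be common, in which case a sentence would settle them. The restriction is not itself at fault.

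It does not remove the point. The restrictive sentence is explicit, gives its reason, and comes after the broad one in the same paragraph, so a reader may fairly take it as the operative rule. Even on the broad reading, the exemptions apply to one source only.

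A reader might go further and infer that the reports will give false reassurance about mobilisation. The documents do not support this: 5.5 uses both sources for the safety description, so events found in the notes would still appear. A reader might also infer that the check on whether the adverse event tool captures all unsafe events would rest on note review alone. That is not supported either: 5.5 bases the check on rehabilitation adverse events as well as SAEs, and clinicians record the former prospectively.

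**Conclusion.** The inconsistency is real and worth correcting. On the restrictive sentence of 7.2, SAEs of mobilisation fall outside the second source, and the comparison planned in 5.5 would reflect what each source may collect. On the rest of section 7 the comparison is recoverable but not fully specified.

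The conclusion rests on mobilisation being routine care, as section 3 states. It does not depend on which reading the sponsor intended, and no view is taken on which reporting rule is right.

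The consequence is modest. The analysis in section 8 is descriptive. No success criterion is attached to SAEs, and section 5.1 treats the criteria that do exist as indications to consider further work. The key outcomes in section 5.3, hypothetical recruitment and day-60 follow-up, are unaffected. Figure 1 is not shown in the available text. Its key mentions AEs and SAEs, so it may clarify the intended source, but it could not remove the sentence in 7.2.

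**What to change.** Reconcile sections 5.5, 7.2 and 7.2.2 so that they agree on which SAEs enter the reporting channel. The reconciliation should cover both sentences of 7.2 as well as the relatedness step and exemptions of 7.2.2. Then choose one of two courses:

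- **Keep the comparison.** State in 5.5 that both sources use the same SAE definition, the same mobilisation window and the same exemptions.
- **Drop the comparison.** State that the SAE rate in 5.5 comes from note review, and that section 7 reports do not describe the safety of usual care.

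The cost is protocol wording. If the comparison is kept, each report must also be matched to a mobilisation session. No change to sample size or to the key outcomes is needed.

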## 8. STATISTICS AND DATA ANALYSIS

For the quantitative data, descriptive statistics will be used to describe and summarise the outcomes set out above. For example the mean and standard deviation or median and interquartile range for continuous variables and numbers and percentages for categorical variables. All qualitative data will be analysed using qualitative content analysis (Elo and Kyngas, 2008).

Where relevant, secondary analysis may be carried out, using descriptive statistics to describe relevant outcomes in different patient subgroups, for example those subgroups defined in a recent Delphi process carried out by the authors (IRAS project ID: 212066; REC reference: 17/LO/0830).

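### The two adverse event records of each mobilisation treatment are to be described route by route and not linked, so the stated output cannot show which events of a given type each route misses

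*Combined protocol and SAP*

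**What the plan says.** Under section 5.5, when a physiotherapist reviews an enrolled patient on vasoactive drugs, "they will complete an extra proforma in the case notes". If a mobilisation treatment takes place, that proforma includes the new adverse event tool. In parallel, "a case note review will be completed by the research team for each mobilisation treatment of patients receiving vasoactive drugs", and the researcher also records rehabilitation adverse events. Both routes therefore work at the level of the single treatment.

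The comparison of routes is listed as "Description of number and type of rehabilitation adverse events recorded prospectively by the treating clinician and retrospectively by researcher case note review". It is meant to inform the tool's usability and "the most feasible way to record AE's in future research". Section 2, secondary objective 2c item 2, is broader: "To measure whether an adverse event tool captures all unsafe events that occur during or immediately after early mobilisation".

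Two further outcomes in 5.5 bear on this:
- "ICU rehabilitation adverse event rate and SAE rate". Two sources are named for serious events. None is named explicitly for rehabilitation adverse events.
- Loss of information. For clinicians this counts treatments "where the rehabilitation adverse event tool is not completed or incomplete". For researchers it counts treatments where the notes did not allow the tool to be completed. Success is a loss of at most 10%.

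Section 8 plans descriptive statistics, giving as an example "numbers and percentages for categorical variables". The readable text contains no linkage of the two records, no cross-classification, no agreement measure and no rule for discordant records.

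**The concern.** Two records of the same treatments are paired data. A count by type from each route gives only the margins of the paired table. The cells show what one route found and the other did not, and margins do not determine cells.

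This matters because the comparison is to guide the choice of recording method for later research, and objective 2c asks about capture. If the two tallies look alike, a reader may take them as agreement when the events behind them differ. The adverse event rate, wanted under the first primary objective, also depends on whether it is built from one record or from both.

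**Working it through.** The documents state no figure for agreement or capture, so there is nothing to reproduce. The check asks how far the planned tallies fix the overlap between routes.

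**Inputs.** The documents give neither the number of treatments nor the number of events; section 6.3 says mobilisation frequency is uncertain. Assumed instead: N = 50, 100 or 200 treatments, and m = 5 or 10 treatments with an event on each route, all of one event type. The unit is a treatment with or without an event of that type.

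**Formulas.** Let b be the treatments where both routes record the event.
- Clinician only = researcher only = m − b
- Distinct events found by either route = 2m − b
- Each route's share of those = m / (2m − b)
- Neither = N − (2m − b)
- Observed agreement = [b + neither] / N
- Chance agreement = [m² + (N − m)²] / N²
- Kappa = (observed − chance) / (1 − chance)

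**Example, N = 100 and m = 10.** Chance agreement = (100 + 8100) / 10000 = 0.82.

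| Both | Only one route (each) | Neither | Distinct | Share per route | Observed agreement | Kappa | Either-source rate |
|---|---|---|---|---|---|---|---|
| 10 | 0 | 90 | 10 | 10/10 = 100% | 1.00 | 1.00 | 10% |
| 5 | 5 | 85 | 15 | 10/15 = 67% | 0.90 | (0.90 − 0.82)/0.18 = 0.44 | 15% |
| 0 | 10 | 80 | 20 | 10/20 = 50% | 0.80 | (0.80 − 0.82)/0.18 = −0.11 | 20% |

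The route-by-route output is 10 versus 10 in all three rows, and the single-source rate is 10% each time.

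**Other assumed values.** With m = 5, overlaps of 5, 2 and 0 give 5, 8 and 10 distinct events and shares of 100%, 62.5% and 50%. Across the grid, full overlap gives kappa 1.00. Zero overlap gives kappa between −0.03 (N = 200, m = 5) and −0.25 (N = 50, m = 10).

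**Effect of event type.** The tallies are split by type, which limits the overlap: within a type it cannot exceed the smaller of the two tallies. A type found by one route and never by the other would be visible at once. Where the two tallies for a type are similar, the range above stays open within that type.

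**Does loss of information fill the gap?** No. It counts forms that are missing, incomplete or impossible to complete. A fully completed form that omits an event contributes nothing to it, so a route could meet the 10% criterion and still miss events.

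**The case against.** The strongest reply is that this is an exploratory study with deliberately descriptive aims. Its key outcomes are recruitment and follow-up. Feasibility of the tool has its own measures: completion in under 5 minutes, at most 10% loss of information, and a clinician survey. Section 8 offers counts and percentages only as examples, so nothing forbids a cross-tabulation. This is fair, and it limits the weight of the point. None of those measures counts missed events, however, and a cross-tabulation that is merely not forbidden is not planned.

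Several stronger readings are tempting, and the documents do not support them:
- A reader might infer that the study cannot say what each route misses. That is true of the stated output only. Both routes cover the same treatments, so the data could answer the question.
- A reader might infer that equal totals would hide everything. The split by type prevents that.
- A reader might infer that every treatment has two usable records. Section 5.5 itself expects some missing or incomplete ones, so a linked table needs a rule for them.
- A reader might suspect that the routes use different time windows. Section 5.5 describes the period in the same terms for both, so no discrepancy is shown.
- A reader might conclude that the either-source rate has to be the headline, because one source understates harm. That treats every unconfirmed record as a true event. The list of outcomes directly follows the note-review sentence, so a note-review rate is also a possible reading.

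One objection also limits the remedy. The clinician proforma sits in the notes that the researcher reviews, and no masking is stated. Zero overlap is therefore an outer bound. A reviewer who copies the proforma would tend to empty the clinician-only cell and raise the note-review share without adding independent evidence.

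**Conclusion.** The point holds as a cheap improvement to the analysis. The stated comparison leaves open, within an event type, whether the two routes found the same events, and no other planned measure closes that gap. In the illustration, identical tallies of 10 in 100 treatments are compatible with 10 to 20 distinct events, and with each route capturing 100% down to 50% of them.

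Those figures rest on assumed counts, equal tallies on the two routes and a single event type. They show a possible range and do not predict the result. Capture here means a share of events found by either route; events missed by both stay unseen. The conclusion covers the readable text only: the case report forms are not included and section 9.3.2 is partly redacted.

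**What to change.** In sections 5.5 and 8:
1. Link the clinician and researcher records by treatment and event type.
2. Among treatments with both records complete, report both, clinician only, researcher only and neither. Count treatments with only one usable record separately.
3. Give each route's share of the events found by either route.
4. Show the adverse event rate by clinician record, by note review and by either source, side by side and labelled by source.
5. State whether the reviewer could see the completed clinician proforma, and read the agreement accordingly, since sight of it would inflate agreement.

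The cost is one small extra descriptive table. With at most 40 patients it will rest on few events, so the shares will be imprecise and should be shown with their counts. No new data are needed, because both records are already planned at treatment level.
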